2.8 Primary and secondary outcome measures

The primary outcome is subjective symptom improvement (evaluated by the prolapse domain score of the Deutsche Beckenboden Fragebogen) assessed at 12 months after surgery.

The secondary outcomes are the anatomical outcomes (the rate of suboptimal anatomical outcome in each compartment (POP-Q point, change in POP-Q values from baseline), condition-specific quality of life (any changes in questionnaire Deutscher Beckenboden Fragebogen from baseline), postoperative complications (haematoma, vesico-vaginal fistula, ureteral obstruction, urinary tract infection, incomplete bladder emptying, overactive bladder or stress incontinence symptoms, suture erosion, vaginal wound dehiscence, infection or granulation tissue, etc), and use of pain killers during the hospital stay. In addition, patients' pain level will be assessed through the standardised Visual Analog Scale (VAS), Numeric Rating Scale (NRS) [13] and the earlier specified questions, patients' improvement rate will be assessed through the "Patient Global Impression of Improvement (PGI-I).

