2.1 Study hypothesis

Primary study hypothesis is that patients receiving a sacrospinous hysteropexy with non-resorbable Prolene sutures (study group) experience a better subjective symptom improvement (evaluated by the prolapse domain score of the Deutscher Beckenboden Fragebogen [11]) assessed at 12 months after surgery, than patients with resorbable PDS sutures (control group).

The secondary hypotheses are, that the study group will have:

- better anatomical outcomes (better rate anatomical outcome in each compartment (change in POP-Q values from baseline) [12]),
- better condition-specific quality of life scores (changes in questionnaire from baseline),
- less postoperative complications (haematoma, vesico-vaginal fistula, ureteral obstruction, urinary tract infection, incomplete bladder emptying, overactive

bladder or stress incontinence symptoms, suture erosion, vaginal wound dehiscence, infection or granulation tissue, etc),

- lower use of pain killers for buttock pain during the hospital stay and in the 12 months postoperative period
- lower pain levels (assessed through the standardised Visual Analog Scale (VAS) and Numeric Rating Scale (NRS) [13]) at postoperative day 1, at discharge, at 4 to 6 weeks, 6 and 12 months.

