2.8 Data collection

At baseline, the following data will be collected: demographics and medical history data (age, body mass index, parity, menopausal and hormone therapy status, nutritional status, current smoking, previous hysterectomy and previous anti-incontinence surgery), and medical comorbidities (diabetes mellitus, connective tissue disorders), and data from the standardized urogynaecologic examination (POP-Q examination during maximal Valsalva, genital hiatus measurements and ultrasound of cervix, uterus, bladder, pelvic floor muscles and levator ani muscle hiatus).

Urogynaecologic examination evaluations is made using the POP-Q measurement system on maximum Valsalva effort in the seated semi-lithotomy position (a 45° upright sitting position). Objective anatomical cure is defined as a Ba point < -1. Symptoms, quality of life and sexuality are evaluated with the Deutscher

Beckenboden-Fragebogen. This Pelvic Floor Questionnaire consists of four domains: bladder, bowel, pelvic organ prolapse and sexual function. In every domain various questions assess severity and condition-specific quality of life. Every question is scored on a scale from zero to four. The sum of each individual domain is divided by the maximum reachable score and multiplied by ten, giving a value between zero (0=no symptoms) and ten (10=maximum of symptoms) for each of the domains. Baessler et al. has published the results of the validation study and scoring system [11].

To evaluate nutrition status, patients will receive the "Mini Nutritional Assessment"-Fragebogen (<https://www.dgem.de/sites/default/files/PDFs/Screening/MNA-SF%20Deutsch-240513.pdf>) and laboratory testing of albumin, electrolytes (sodium, potassium, magnesium, phosphate, and calcium), haematocrit, creatinine, blood urea nitrogen, and bilirubin.

Patients will be asked to complete the standardised Visual Analog Scale (VAS), Numeric Rating Scale (NRS) [13] and answer the following questions:

- "Do you experience a sensation of bulging or protrusion from the vagina?" and "Do you have a bulge or something fallen out that you can see in the vagina?" [6]
- "Do you experience pain in the rump?" and "Do you experience pain in the lower back?" and "Do you experience pain while walking?" [6]
- "What rate of postoperative recurrence would you accept and still opt for the surgery?" [14].

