2.10 Data analysis

Statistical analysis will be performed using SPSS and Excel software. Data will be calculated and graphed as mean plus minus standard error of mean (SEM).

Metric variables will be reported by mean and standard deviation resp. median and IQR, categorical variables will be reported by frequencies per group and timepoint. The primary outcome subjective symptom improvement after 12 months in either group will be analyzed by a t-test or a Man-Whitney-U-test depending on the distribution of improvements.

For the secondary endpoints, differences of rates of adverse events between the two treatment groups will be analysed by a Chi-squared test. Blood loss, use of pain killers and changes in condition-specific quality of life will be compared between groups analogously to the primary outcome.

Changes in POP-Q values from baseline over time will be analysed by a linear mixed model with fixed effects group, time, POP-Q point, age and BMI and random effect intercept per patient. Statistical significance will be set 0.05. No correction for multiple testing is performed because only one main hypothesis is considered.

3. Research facility

The patient screening will be performed at the urogynaecologic outpatient clinic of the Department of General Gynaecology and Gynaecologic Oncology, Medical University of Vienna, Austria. Infrastructure needed for this study is already present.

4. Ethical and legal aspects

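### The plan declares an anatomical rate as a secondary outcome but specifies a between-arm analysis only for POP-Q change, and that model does not report by compartment

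*Combined protocol and SAP*

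**What the plan says.** The section on primary and secondary outcome measures lists, as the anatomical secondary outcome, "the rate of suboptimal anatomical outcome in each compartment (POP-Q point, change in POP-Q values from baseline". Section 2.1 states the matching hypothesis as "better rate anatomical outcome in each compartment (change in POP-Q values from baseline". Both put a rate and a continuous change into one bracketed phrase.

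The data collection section gives the only anatomical limit in the document: "Objective anatomical cure is defined as a Ba point < -1". It is not linked to the secondary outcome or to any analysis.

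Section 2.10 has four sentences that bear on the point:

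- The anatomical analysis: "Changes in POP-Q values from baseline over time will be analysed by a linear mixed model". Its fixed terms are treatment arm, visit, which POP-Q point was measured, and the covariates age and body mass index; each patient has a random intercept. No interaction is listed.
- The only test of proportions is for safety: "differences of rates of adverse events between the two treatment groups will be analysed by a Chi-squared test".
- Blood loss, analgesic use and quality-of-life changes are compared in the same way as the primary outcome. Anatomy is not in that list.
- For description, "categorical variables will be reported by frequencies per group and timepoint".

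**The concern.** A proportion with a suboptimal result and a mean change in centimetres are different endpoints, and neither determines the other. If section 2.10 is followed as written, a declared secondary outcome ends with no between-arm estimate. Because the limit is undefined outside the anterior compartment and no visit is fixed, anyone who later wants to compare the rate must choose both, possibly after seeing the data.

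The second gap lies in the model itself. The outcome is stated for each compartment, but the listed terms give one group effect pooled over POP-Q points and visits. The per-compartment question is therefore left open for the change as well as for the rate.

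**Working it through.** **1. The declared outcome against the planned analysis**

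| Element | Rate | POP-Q change |
|---|---|---|
| Named in 2.1 and in the outcomes section | yes | yes, in the same bracket |
| Defined | no limit for suboptimal; Ba < -1 is called cure, anterior only | yes, difference from baseline |
| Timepoint | none | all visits together |
| Between-arm analysis in 2.10 | none | linear mixed model |
| Reported by compartment | not specified | no, main effects only |

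**2. Why the mean does not stand in for the rate.** The values here are assumed, because the documents give no anatomical results. Take equal baselines, so that a difference in 12-month means equals a difference in change, and count Ba of -1 or above as suboptimal.

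- Same rate, different means. Both arms have 30% at Ba = 0; the other 70% sit at -2 in one arm and -3 in the other. Means: 0.7 × (-2) = -1.4 and 0.7 × (-3) = -2.1. The difference is 0.7 cm, yet the rate is 30% in both.
- Same mean, different rates. One arm is as above (30% at 0, 70% at -2; mean -1.4). The other has 10% at 0 and 90% at -1.4/0.9 = -1.56; its mean is also -1.4. The rates are 30% and 10%.

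**3. What the mixed model estimates.** Write the true group effects on change at the anterior, apical and posterior points as a, b and c. With a group main effect only, complete data and one point per compartment, the group coefficient estimates (a + b + c)/3, itself averaged over the three follow-up visits (4 to 6 weeks, 6 months, 12 months). It gives neither a, b and c separately nor the 12-month effect.

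**4. Number of women available.** The plan's own figure, for the primary outcome in section 2.9, reproduces:

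- SD of change = √(2 × 2.2² × (1 − 0.5)) = 2.2.
- A difference of 2 is a standardised effect of 2/2.2 = 0.91. A two-sided t-test at 0.05 with 80% power needs 20.002, so 21 per arm; power at 21 is 0.82.
- With 26 randomised and 20% dropout, 26 × 0.8 = 20.8 remain.

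So 21 evaluable women per arm is realistic, and 26 is the ceiling.

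**5. Precision and power for an added rate comparison.** The level comes from "Statistical significance will be set 0.05"; sidedness is not stated, so two-sided is assumed. The rates are assumed. With d = p1 − p2 and p̄ their mean, power = Φ{[d√n − 1.96√(2p̄(1−p̄))] / √(p1(1−p1) + p2(1−p2))}. For 30% v 10% and n = 21: (0.2 × 4.583 − 1.109)/0.548 = −0.35, and Φ(−0.35) = 0.36.

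| Assumed rates | Power, n = 21 | Power, n = 26 | n per arm for 80% |
|---|---|---|---|
| 50% v 30% | 0.26 | 0.31 | 93 |
| 40% v 20% | 0.29 | 0.35 | 82 |
| 30% v 10% | 0.36 | 0.44 | 62 |
| 30% v 15% | 0.21 | 0.25 | 121 |
| 20% v 10% | 0.14 | 0.17 | 199 |

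Exact enumeration of the uncorrected chi-squared test gives slightly higher values (0.378 and 0.469 for 30% v 10%); Fisher's test gives lower ones (0.259 and 0.322). A wider gap of 40% v 10% reaches 0.62 and 0.72.

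The 95% CI half-width, with the same rate p in both arms, is 1.96√(2p(1−p)/n). At n = 21 it is 0.242 for p = 20%, 0.277 for 30% and 0.296 for 40%, that is, 24 to 30 percentage points.

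**The case against.** The strongest reply is that the bracket tells the reader what was meant. If POP-Q change is the intended measure, the planned model matches it and the word rate is loose drafting. Alternatively, the brackets in the outcomes section do not balance (two open, one closes), so the text may list two outcomes, of which the second is analysed. Both readings are possible and the documents do not settle between them. Neither removes the problem. On the first, the wording of two sections is wrong; on the second, one of two declared outcomes has no comparison. On both, the model still does not report by compartment.

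It is also fair to say that this is one secondary outcome in a plan with a single main hypothesis, and that an added rate comparison has little power. That stands as a reason to present it as estimation. It is not a reason to leave the outcome without an estimate.

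Some stronger inferences should be resisted:

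- A reader might infer that the rate will go unreported. The rule on frequencies for categorical variables would allow a descriptive table by arm and visit, provided the category were defined.
- A reader might infer that the hypothesis counts women with poor results. Section 2.1 speaks only of a better rate; suboptimal appears only in the outcomes section.
- A reader might infer that the authors will present a mean shift as fewer failures, or that rate and change would favour different arms. Nothing in the documents says the first, and they contain no anatomical data from which to judge the second.

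**Conclusion.** The mismatch is in the text and rests on no assumed figure. The outcomes section declares an anatomical rate for each compartment, and section 2.10 specifies a between-arm estimate only for POP-Q change, pooled over points and visits. Suboptimal is undefined, no timepoint is set, and the one existing limit covers the anterior compartment only.

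The size of the consequence cannot be derived from the documents, because they give no anatomical rates. What can be said is how little a repaired comparison could show: for the assumed rates in the table, power is about 0.14 to 0.44 with 21 to 26 women per arm, and the interval half-width with 21 per arm is about 24 to 30 points for rates of 20% to 40%. The primary outcome, its analysis and the sample size are unaffected. The point deserves correction before unblinding, at the level of a secondary outcome.

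**What to change.** 1. In section 2.1 and in the outcomes section, list the rate of suboptimal anatomical outcome and the change in POP-Q values as two separate outcomes, and close the brackets.
2. Define suboptimal for each compartment. For the anterior compartment, use the protocol's existing Ba limit and say explicitly that women not meeting it count as suboptimal. For the apical and posterior compartments, the investigators should set the limits and record them before unblinding.
3. In section 2.10, add for each compartment the between-arm risk difference at 12 months with a 95% CI. Use an exact or score-based interval, since counts may be small (10% of 21 is about two women). Label the comparison as estimation, and say that an interval including zero does not show equivalence.
4. Name the POP-Q points that enter the mixed model, add group-by-point and group-by-time terms, and report the 12-month difference in change for each compartment. With two-way terms alone, the contrast between points is assumed equal at every visit; point-by-time and three-way terms would remove that assumption.

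If the investigators intend POP-Q change only, they can instead remove the rate from both sections, document this before unblinding, and make only the fourth change.

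The cost is a wording amendment and one extra table; POP-Q is already measured at every follow-up visit. The drawbacks are wide intervals for the rates and more parameters in the mixed model.

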2.9 Sample size and power considerations

Alteration of the prolapse domain score obtained from the pelvic floor questionnaire before and after intervention (between baseline and 12 months follow-up) will be compared between patients receiving continuous stitches versus simple interrupted stitches for anterior colporrhaphy. Schoenfeld et al. observed a mean prolapse domain score of 3.33 with a standard deviation of 2.2; we assume that the standard deviation of the pre- and post-interventional treatment will be equal, and that the correlation between the two values is 0.5, resulting in a standard deviation of the change between pre- and post-interventional value will be 2.2.; then, with 21 patients per group a difference of 2 between the changes in the two groups can be identified

with 80% power. Taking into account an expected dropout rate of 20%, 26 patients will be included per group.

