2.2 Study design

This trial is a single-centre, prospective, randomized trial conducted with the aim of determining the superiority of non-absorbable prolene over absorbable PDS suture material with regard to the primary outcome in POP patients undergoing sacrospinous hysteropexy. The study will be a single-blind study, as it is impossible to blind the study surgeon for the surgical procedure to which the subject is assigned. However, all outcome assessors and the subjects will be blinded to the assigned treatment. Postoperative follow-up will take place after 4-6 weeks, 6 months and 12 months. Patients will undergo a standardized urogynaecologic examination that includes assessment of prolapse with POP-Q measurement [12]. Furthermore subjective outcome will be assessed with standardized questionnaires – our study participants will receive the German version of the pelvic floor questionnaire [11].

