Furthermore, patients will answer the "Patient Global Impression of Improvement (PGI-I)" as it takes little effort for the patient and allows a precise result in terms of the rate of improvement after the operation [15]. One of the following answers can be given by each patient:

1. A lot better.
2. Much better.
3. A little better.
4. no change.
5. A little worse.
6. Much worse.
7. A lot worse.

Scheduled in-person follow-ups will occur at 4 to 6 weeks, 6 and 12 months after the operation. Each check-up will include a full urogynaecologic clinical examination including POP-Q, ultrasound and bloodwork as well as a written questionnaire identical to the one at baseline. In addition, an update of current medications, an assessment of new or continuing pelvic floor disorders and adverse events that occurred since the previous evaluation will be obtained by the study coordinator at each visit. All data will be anonymized and collected using case report forms by examiners or trained research coordinators who are blinded to the treatment assignment.

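### The primary test of 12-month change has no missing-data method, so with 20% dropout about 5 of 26 women per arm would not enter it, although their earlier scores are collected

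*Combined protocol and SAP*

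**What the plan says.** All references are to the combined protocol and SAP.

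- Section 2.9 defines the primary comparison as the change in prolapse domain score from baseline to 12 months. It plans that "with 21 patients per group a difference of 2 between the changes in the two groups can be identified" at 80% power.
- On dropout, section 2.9 says only: "Taking into account an expected dropout rate of 20%, 26 patients will be included per group".
- Section 2.10 gives the analysis: "The primary outcome subjective symptom improvement after 12 months in either group will be analyzed by a t-test or a Man-Whitney-U-test", the choice depending on the distribution of improvements.
- Section 2.8 (Data collection) schedules visits at 4-6 weeks, 6 months and 12 months, each with "a written questionnaire identical to the one at baseline". The prolapse domain score is therefore due twice after surgery before the primary time point.
- Section 2.10 uses a linear mixed model for POP-Q values over time, but not for the primary score.
- No section defines an analysis population, a rule for missing primary scores, imputation, or a sensitivity analysis for dropout.

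**The concern.** Both named tests need one change value per woman, and that value needs a 12-month score. With no missing-data method, a woman lost after her 6-month visit leaves the primary analysis, and so do the baseline score and the two post-operative scores she has already given.

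Two things are at stake:

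- **Efficiency.** In a trial of 52 women, the raw change score makes poor use of the baseline value and no use of the intermediate visits.
- **Validity.** Enrolling extra women replaces lost numbers, not the particular women lost. If women stop attending because of how their prolapse is doing, and this works differently in the two arms, the completers no longer give a fair comparison. The earlier scores could correct part of that, and the planned test ignores them.

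**Working it through.** **Inputs from the documents.** Section 2.9: "observed a mean prolapse domain score of 3.33 with a standard deviation of 2.2"; "the correlation between the two values is 0.5"; target difference 2; 21 evaluable and 26 enrolled per arm; 20% dropout. Section 2.10: "Statistical significance will be set 0.05". Sidedness is not stated; two-sided is assumed.

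**Inputs assumed.** The correlation r between post-operative scores (0.5 to 0.8), the timing of dropout, and the dropout mechanism. The documents give none of these.

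**Step 1: the plan's own figures.**
- SD of change = √(2 × 2.2² × (1 − 0.5)) = 2.2, as stated.
- Two-sided 5%, 80% power, difference 2: 19 per arm by normal approximation. By the exact noncentral t, 20 per arm gives 80.0% and 21 gives 82.0%. The stated 21 is reproduced.
- Dropout: 21 × 1.2 = 25.2, rounded up to 26; 21 / 0.8 = 26.25, rounded up to 27. Expected completers are 26 × 0.8 = 20.8. The one-patient difference is immaterial.

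**Step 2: who is left out.** 26 − 21 = 5 per arm, about 10 of 52.

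**Step 3: precision and power for a true difference of 2** (normal approximation, two-sided 5%, 21 completers of 26 per arm).
- t-test on change: SE = 2.2 × √(2/21) = 0.679. Power = Φ(2/0.679 − 1.96) = 83.8%.
- Baseline-adjusted analysis (ANCOVA) of the same 21 completers: SE = 2.2 × √(1 − 0.5²) × √(2/21) = 0.588. Power 92.5%.
- Repeated-measures likelihood model with baseline adjustment, dropouts having at least the 4-6 week score: SE 0.582 to 0.552 and power 93.0% to 95.2%, as r goes from 0.5 to 0.8.
- The same model without baseline adjustment: SE 0.657 to 0.631, power 86.1% to 88.7%.

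Baseline adjustment adds 92.5 − 83.8 = 8.7 percentage points. The earlier visits then add 0.5 to 2.7 points.

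**Step 4: possible bias among completers.** If 20% of one arm is missing, and those women differ by D points in mean change from that arm's completers, the estimated difference shifts by 0.2 × D: 0.2 for D = 1, 0.4 for D = 2, 0.6 for D = 3.

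Dropout that depends on the 6-month score matters only if that score is related to the change. With equal SDs, their covariance is 2.2² × (r − 0.5), which is zero at r = 0.5. Large-sample simulation (600,000 per arm, 20% dropout, log-odds of dropout changing by 1 or 2 per SD of the 6-month score) gave this absolute bias of the complete-case difference:

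| r (assumed) | Same mechanism in both arms (log-odds 1) | Score-dependent in one arm only | Opposite directions in the two arms |
|---|---|---|---|
| 0.6 | about 0 | 0.03-0.06 | 0.08-0.12 |
| 0.7 | about 0 | 0.08-0.11 | 0.15-0.23 |
| 0.8 | about 0 | 0.12-0.17 | 0.23-0.35 |

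With all correlations at 0.5, the bias was about 0 in every pattern run. A likelihood estimate using the earlier scores was within 0.01 of the truth throughout. That is expected, because dropout was generated from an observed score and so was missing at random by design. Swapping the arms reverses the sign of the bias.

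**The case against.** **The plan never says that women are dropped.** This is fair. The term complete case does not appear, and a t-test can be run after multiple imputation. A reader might infer that the plan prescribes a complete-case analysis. It does not: the exclusion follows only because no other method is stated. What stands is that a woman without a 12-month score has no stated route into the primary test.

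**Power is already protected.** This is also correct. A reader might infer that the trial is underpowered because of dropout. Step 1 shows that it is not: 21 completers per arm give 82.0% by the exact t.

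**The efficiency gain is mostly not about dropouts.** This stands too. It would be wrong to credit the rise to 93-95% to recovered dropouts, since ANCOVA in completers alone reaches 92.5%.

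**The bias is hypothetical.** Nothing in the documents shows that dropout will differ by arm, and section 2.2 blinds the women and the outcome assessors. The only correlation given is the 0.5 between pre- and post-operative scores, and at 0.5 throughout the bias vanishes. A reader might infer that the planned estimate is biased, or biased against prolene. The documents support neither. Blinding makes differential dropout less likely but does not exclude it, since women respond to their own symptoms.

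**The model has limits.** It cannot recover much for women with no post-operative score, and the documents do not say when dropout will occur. The score is bounded at 0 to 10, so normality is only approximate.

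**Conclusion.** The point holds as a weakness in the choice of analysis that should be corrected. It is not an error in the sample size and not evidence that the result will be wrong.

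With no missing-data method stated, about 5 of 26 women per arm would not enter the primary test, while scores already scheduled go unused.

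- **Efficiency.** A baseline-adjusted repeated-measures model lowers the SE from about 0.68 to 0.55-0.58. Most of that comes from baseline adjustment, which rests on the plan's own correlation of 0.5. The smaller contribution of the earlier visits rests on assumed post-operative correlations of 0.5-0.8. These power figures use the normal approximation and will be slightly lower with small-sample degrees of freedom.
- **Bias.** It is 0 if dropout works alike in both arms or all correlations are 0.5. It reaches about 0.3-0.35 point, in either direction, if dropout depends on the score in opposite ways in the two arms and the post-operative correlation is as high as 0.8. Against a target difference of 2, that is at most about 17% (0.345/2). Dropout that depends on unobserved outcomes is not covered by these figures.

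**What to change.** Amend section 2.10 before outcome data are examined by arm.

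1. **Population.** State that all randomised women are analysed as allocated.
2. **Primary analysis.** Use a likelihood-based repeated-measures model of the prolapse domain score at 4-6 weeks, 6 months and 12 months. Fixed effects are arm, visit, arm-by-visit, baseline score, baseline-by-visit and parity stratum, with unstructured covariance and small-sample degrees of freedom. The primary estimate is the arm difference at 12 months with its 95% confidence interval.
3. **Sensitivity analyses.** Keep the t-test or Mann-Whitney test on observed 12-month change, which also checks the result against non-normality of the bounded score. Add a delta-adjusted analysis for data missing not at random.
4. **Reporting.** Report the number and timing of missing scores by arm.

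Multiple imputation using the earlier scores, followed by a baseline-adjusted comparison, would be an acceptable alternative.

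The cost is SAP wording only: no extra women, visits or questionnaires, and SPSS, which the plan names, fits mixed models. The downside is reliance on missing-at-random and approximate normality, with little recovery for women who have no post-operative score.
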